Protocol and Statistical Analysis Plan

Official Title: **Brief Online Interventions for Alcohol Use (Mechanical Turk 10)**

NCT Number: **NCT03438539**

Document Date: **February 22, 2018**

Coversheet Created On: **November 26, 2019**

RESEARCH PROCEDURES

This experiment will consist of a battery of self-report questionnaires about health behaviors and alcohol use. Subjects will be told that the purpose of the study is to learn about the effects of cognitive training. Other than this general explanation of purpose, subjects will not be given any information concerning what outcomes might be expected.

Screening Questions (Appendix B). To determine whether subjects qualify, a short screening questionnaire will be used in which subjects answer questions about their age, sex, and drug use behaviors. Namely, subjects will be asked if they used alcohol, cigarettes, and marijuana in the past week to conceal the specific drug use qualifications. Subjects will also complete a questionnaire evaluating DSM-V criteria for alcohol use disorder. If a subject fails to qualify based on the inclusion criteria stipulated above (see Study Population), he or she will be thanked for his or her time and provided \$0.05 compensation for completing this screener.

Phase 1: Baseline Survey. Subjects will first complete a baseline phase in which a health and drug use history is collected. Approximately half of subjects will also be randomized to receive normative feedback on alcohol use as a part of the baseline survey (see Normative Feedback below).

Alcohol Use History. Subjects will complete a battery of standardized assessments of alcohol use, such as the Alcohol Use Disorder Identification Test (AUDIT), Drinker Inventory of Consequences (DrInC), and timeline follow back for the past two weeks of alcohol use (TLFB). These measures are designed to capture past and current alcohol use behaviors and severity (e.g., drinks consumed per week, past month binge alcohol use). The Readiness for Change questionnaire evaluating desire and readiness to change alcohol use behaviors will also be collected (Rollnick et al., 1992). However, no exclusion criteria based on desire or readiness to change alcohol consumption will be used.

Behavioral Economic Measures (Appendix C-E). Subjects will complete a battery of behavioral economic measures, including a delay discounting task (Koffarnus & Bickel, 2014; Appendix C), commodity purchase task (Murphy and MacKillop, 2006; Appendix D), and a Reinforcement Survey Schedule-Alcohol Use Version (Murphy et al., 2005; Appendix E). These measures have been extensively applied in the behavioral science literature to evaluate aspects of alcohol valuation and reinforcement (Amlung et al., 2015; Murphy and MacKillop, 2006; Cox and Dallery, 2016; Koffarnus and Bickel, 2014; Morris et al., 2017). We have also effectively used these measures on the mTurk platform in previous research (Strickland & Stoops, under review; Strickland & Stoops, 2017; Strickland et al., 2017).

Normative Feedback (Appendix F). Half of subjects will be randomly assigned to a normative feedback condition. Subjects assigned to this condition will be directed to a statement standardized based on subjects' reported average number of standard drinks per week, age, and gender. This statement will provide a normative comparison of alcohol consumption to individuals of the same age and gender (see Appendix F for example). Percentile ranks for the normative comparisons will be made using data from the 2016 National Survey on Drug Use and Health (Center for Behavioral Health Statistics, 2017). After receiving feedback, subjects will report perceptions of this feedback (e.g., was it surprising, helpful, expected) as well as motivation to change alcohol use in response to the feedback. Previous studies have shown the feasibility and acceptability of delivering this type of normative feedback through mTurk (Kuerbis et al., 2016; 2017). Control participants will receive feedback on time spent doing a non-alcohol related activity as an attention/informational control (e.g., time spent watching television; LaBrie et al., 2013). Control subjects will complete feedback perception questions for the provided information, similar to the alcohol normative feedback group.

Demographic and Other Drug Use Variables: A battery of standardized questionnaires will assess other drug use and health behavior (e.g., DAST for substance use severity; FTND for cigarette use severity). Demographics will be also collected for each subject, including items such as age, sex, race, and education.

Phase 2: Cognitive Training Phase. Following completion of the baseline phase, subjects will be contacted through mTurk's interface to complete a 2-week cognitive training study. Subjects will be asked to complete daily cognitive training surveys and told that they will receive \$0.50 for each 5-8 minute survey completed. Additionally, subjects will be told that completion of 10 or more assessments will result in entry into a raffle for one of five \$50 bonuses.

Subjects will be randomly assigned to one of three training conditions using stratified sampling. Sampling will be stratified based on alcohol use disorder status (e.g., moderate, severe) to ensure equal representation in each condition. All training conditions will be completed daily and will take ~5-8 minutes to complete. Tasks will be programmed in PsyToolkit, an open-source web-based platform that provides reliable reaction time data for online delivery (Stoet, 2017). Recent research in our laboratory has effectively used PsyToolkit for

completing cognitive-behavioral research and demonstrates the feasibility of using the resource for conducting research through mTurk (Lile et al., in preparation).

Inhibitory Control Training (Appendix G). The inhibitory control training task is a modified version of the Cued Go/No-Go tasks (Weafer and Fillmore, 2012; Miller et al. 1991) and is based on a task currently used in our laboratory targeting cocaine inhibitory control. The task will take approximately 5 minutes to complete and will consist of 2 blocks of 50 trials. A trial will involve a sequence of events during which a fixation point (+) will be presented for 800 ms, followed by a blank white screen for 500 ms, a cue image (alcohol or neutral) will be presented for one of five stimulus onset asynchronies (SOA; i.e., 100, 200, 300, 400, 500 ms), and finally a go or no-go target, which will be displayed until a response occurs or 1000 ms elapses. There will be a 700 ms interval between all trials. Alcohol images will serve as no-go cues and visually matched neutral images will serve as go cues. Cues will predict which target will be presented 100% of the time. After a SOA, the cue will either turn solid green (go target) or solid blue (no-go target). Subjects will be instructed to press the SPACE bar on the keyboard as soon as a green (go) target appears. Subjects will be instructed to withhold responses when a blue (no-go) target appears.

Working Memory Training (Appendix H for example). A battery of working memory tasks will be used during the intervention period. These tasks were selected from previous research evaluating working memory training in substance use disorder (Bickel et al., 2011b; Houben et al., 2011b). Tasks will include visuospatial working memory task, digit span task, letter span task, and the n-back task. Broadly speaking, these tasks require information recall and/or categorization of that information based on short-term retention. Task difficulty varies within each task and increases or decreases based on task performance. Subjects will complete one task randomly selected from the possible tasks during each session. Expected time of completion is 5 minutes.

Control Training Tasks. Control training tasks will include completion of basic arithmetic problems for approximately 5 minutes. These problems will include simple one digit arithmetic and are intended to control for engagement with the training session, but with a task that is unrelated to response inhibition or working memory training.

Alcohol Use Measures (Appendix J). All subjects will also report on the previous day's alcohol use and alcohol craving during each training session.

Phase 3: Follow Up Phase.

Post-Training Follow Up. Subjects will be asked to complete a post-training follow up survey. This survey will be identical to the baseline survey and will evaluate changes in the alcohol use, behavioral economic, and other cognitive-behavioral measures over the course of the 2-week training period.

The post-training follow up will also contain acceptability measures. The Treatment Acceptability Questionnaire will be administered and subjects will rate their response to statements on a 100-point visual analog scale (0 = Low; 100 = High) (e.g., ease of completion, helpful instructions, enjoyability). Multiple choice questions will also be used to evaluate how much subjects would pay to participate in the tasks completed in the study, if they would participate again, and motives related to study participation (e.g., to make money, to reduce alcohol use). Qualitative measures will also be included to collect features not captured by these quantitative measures (e.g., "What did you like most/least about the study?"). These measures were derived from prior research delivering behavioral interventions through online platforms (e.g., Raiff et al., 2013)

Two-Week Follow Up. Subjects will be asked to complete a 2-week follow up survey. This survey will include alcohol use and severity measures as well as 2-week timeline follow back from the end of the intervention period.

Data Analysis (Statistical Analysis Plan)

All statistical analyses will be conducted in R programming using two-tailed tests and an alpha rate of 0.05.

Feasibility. Descriptive statistics will first be used to express study attrition (i.e., the primary measure of feasibility). Feasibility will be supported by average completion rates during the intervention period greater than 80%. This value was selected given the general target of greater than 80% when evaluating adherence to pharmacological interventions (see Brown & Bussell, 2011). Predictors of attrition will also be evaluated using multiple regression (% completed assessments) or time-hazard models (time to first missed assessment).

Acceptability. Descriptive statistics will first be used to express acceptability measures. The primary outcome will be percentage of subjects reporting they would participate again. Success will be defined greater than 80% subjects reporting they would participate again in each active intervention condition. This value was selected for consistency with the feasibility benchmark selected. Other measures will be compared between cognitive-training conditions (e.g., enjoyability) using a one-way between-subjects ANOVA. Other predictors of acceptability will be evaluated using multiple regression (continuous outcomes) or logistic regression (dichotomous outcomes).

Initial Efficacy and Moderating Variables. Mixed-effect modeling (i.e., multilevel modeling) will be used to evaluate intervention effects on alcohol use. The primary outcome will be subjects with no heavy drinking days (dichotomous). This criterion was recently selected by the FDA as an acceptable clinical trial endpoint for FDA-approval of medications. Secondary outcomes will include changes in behavioral economic measures and other alcohol use variables by treatment condition. Secondary analyses will also be conducted evaluating baseline measures as prognostic variables predicting changes in alcohol consumption.

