Appendix A

DSM-V Alcohol Use Disorder Questionnaire (from Hagman, 2017)

Below are questions related to your experiences from alcohol use within the past year. Please select your best answer to each question as to whether each experience occurred more than once in the prior year in response to your alcohol use. REMEMBER TO SELECT YOUR BEST ANSWER.

1. During the past year, were you unable to or failed to fulfill major role obligations at work, school or home because of alcohol use?

YES

NO

2. During the past year, did you consume alcohol in situations in which it was physically hazardous (e.g., driving while intoxicated)?

YES

NO

3. During the past year, did you continue to drink alcohol despite persistent or recurrent social or interpersonal problems caused by the effects of the alcohol (e.g., arguments with a significant other or family member, physical fight)?

YES

NO

4. During the past year, as a result of your drinking, did you have a need to drink more to become intoxicated or get the desired effect?

YES

NO

5. During the past year, as a result of your drinking, did you notice a diminished effect with continued use of the same amount of alcohol?

YES

NO

6. During the past year, as a result of your drinking, did you experience any withdrawal symptoms from not drinking (e.g., shakes, tremors, sleeplessness, anxiety, sweating, flushing)?

YES

NO

7. During the past year, as a result of your drinking, did you drink to relieve or avoid withdrawal symptoms?

YES

NO

8. During the past year, did you drink alcohol in larger amounts or over a longer period than intended?

YES

NO

9. During the past year, as a result of alcohol use, did you have a persistent desire or have unsuccessful efforts to cut down or control alcohol use?

YES

NO

10. During the past year, as a result of alcohol use, did you spend a great deal of time in activities necessary to obtain alcohol or recover from its effects?

YES

NO

11. During the past year, as a result of alcohol use, were important social, occupational, or recreational activities given up or reduced because of alcohol use?

YES

NO

12. During the past year, as a result of alcohol use, did you continue to drink alcohol, despite knowledge of having a persistent or recurrent physical or psychological problem that is likely to have been caused or exacerbated by drinking?

YES

NO

13. During the past year, as a result of alcohol use, did you have a strong desire or craving to drink?

YES

NO

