APPENDIX B
Screening Questionnaire

1. What is your age?

2. What is your sex?

Male

Female

3. Have you drunk an alcoholic beverage in the past week?

Yes

No

4. Have you smoked a cigarette in the past week?

Yes

No

5. Have you used marijuana in the past week?

Yes

No

6. Would you be interested in participating in a 2-week study where you complete daily cognitive training tasks. You will be paid for each daily training survey (\$0.50/survey, approximately 5-8 minutes/survey). You will also be entered to win one of five \$50 bonuses based on active participation (e.g., completing > 70% of surveys).

Yes

No

I do not know

7. DSM-V Alcohol Use Disorder Questionnaire (See Appendix A)

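### The screener shows the paid 2-week offer just before the unmasked alcohol use disorder questions; asking those questions first would lower the risk of false qualification at almost no cost

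*Combined protocol and SAP*

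**What the plan says.** The Screening Questions section uses a short form to decide who qualifies. On the past-week drug items it says that "subjects will be asked if they used alcohol, cigarettes, and marijuana in the past week to conceal the specific drug use qualifications". The next sentence adds the disorder questionnaire: "Subjects will also complete a questionnaire evaluating DSM-V criteria for alcohol use disorder". A worker who does not qualify is "thanked for his or her time and provided \$0.05 compensation for completing this screener".

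Appendix B gives the order of the form:
- Items 1 and 2: age and sex.
- Items 3 to 5: past-week alcohol, cigarettes and marijuana.
- Item 6: the offer, which opens "Would you be interested in participating in a 2-week study where you complete daily cognitive training tasks". It continues "You will be paid for each daily training survey", gives the rate of $0.50, and adds "You will also be entered to win one of five" bonuses of $50.
- Item 7: the questionnaire in Appendix A.

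Appendix A is introduced with "Below are questions related to your experiences from alcohol use within the past year" and has 13 yes/no items, all on alcohol. The screener has no matching block for tobacco or marijuana; the FTND and DAST come later, in the baseline survey.

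The Phase 2 section stratifies assignment to training by disorder status, with moderate and severe as examples. It also restates the pay per survey and the raffle.

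**The concern.** Screening answers from paid online workers are unverified self-report. The protocol recognises the hazard, because it disguises which past-week drug use counts. That disguise does not reach the disorder items. By item 7 the worker has read about a paid study and sees that only alcohol problems are being probed. A worker who guesses that entry depends on these answers has a reason to answer YES.

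Three things are at stake:
- **Effect size.** Subjects without the disorder may have little room to change on the primary efficacy outcome, the proportion with no heavy drinking days.
- **Strata.** Appendix A is the only DSM-based measure in the supplied text, so the strata appear to rest on the same answers.
- **Generalisability.** Conclusions are meant to apply to people with alcohol use disorder.

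**Working it through.** The supplied text gives no sample size, power or false-qualification rate, so there is no figure of the plan's to reproduce. The check is of item order, followed by illustrations on stated assumptions.

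**1. Reach of the masking.** Items 3 to 5 come before both the offer and the disorder items, so on a first pass they stay masked. Item 7 comes after the offer and covers one substance. The documents make no concealment claim for item 7.

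**2. What the item 7 answers decide.** The questionnaire is described within the section that determines qualification, and the Phase 2 strata are levels of disorder severity. Both uses are inferred: the screening text sends the reader to Study Population for the criteria, and that section is not supplied. The cut-off is therefore unknown. However, every YES moves towards any minimum symptom count, and YES throughout would reach it.

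**3. Pay in view.** Assuming 14 daily sessions over two weeks:
- Pay: 14 × $0.50 = $7.00, plus the raffle.
- Time: 14 × 5 = 70 minutes to 14 × 8 = 112 minutes.
- Hourly rate: $7.00 ÷ (112/60) = $3.75 to $7.00 ÷ (70/60) = $6.00.

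**4. Attenuation.** Let m be the share of the sample that qualifies falsely and cannot respond, with the same outcome rate in every arm. Then

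observed difference = true difference × (1 − m).

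For an assumed true difference of 15 points:
- m = 5%: 15 × 0.95 = 14.25, about 14.3 points.
- m = 20%: 15 × 0.80 = 12.0 points.

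**5. What that could mean for sample size.** Assume 20% against 35% with no heavy drinking days among genuine cases, a two-sided alpha of 0.05 (the SAP's), 80% power (assumed), and the pooled-variance formula

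n per arm = [1.96·√(2p̄(1 − p̄)) + 0.842·√(p₁(1 − p₁) + p₂(1 − p₂))]² ÷ (p₂ − p₁)².

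Let r be the assumed rate among false qualifiers, the same in both arms. Each arm's rate is (1 − m) × the genuine rate + m × r.

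| m | r | p₁ | p₂ | n per arm |
|---|---|---|---|---|
| 0 | – | 0.200 | 0.350 | 138 |
| 5% | 20% | 0.200 | 0.3425 | 152 |
| 5% | 70% | 0.225 | 0.3675 | 160 |
| 20% | 20% | 0.200 | 0.320 | 209 |
| 20% | 70% | 0.300 | 0.420 | 250 |

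The values of m, r and the 20% and 35% rates are all assumptions. The table shows how the mechanism works and does not estimate what happened in this trial.

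**The case against.** The strongest reply has four parts.

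**The screener does what it claims.** A reader might infer that the form contradicts the protocol's own concealment. The documents do not support that. The concealment sentence is about the past-week items, and those stay masked on a first pass. What stands is that the masking stops short of the disorder items.

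**The incentive is modest and indirect.** Item 6 names no drug and does not say that entry depends on what follows. A reader might set $7.00 against the $0.05 paid for a failed screen and see a 140-fold reward. That compares a short screener with 70 to 112 minutes of work, so it is a poor measure of the motive to misreport. There is still an incentive, and it is disclosed just before the answers that matter.

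**Eligibility and safeguards may lie elsewhere.** Study Population is not supplied. It may set further criteria, attention checks or a block on repeat attempts. This stands, and it is why the point is a risk and not a demonstrated defect. Such safeguards would not change the item order.

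**Randomisation and baseline data limit the harm.** Screening precedes randomisation, so false qualifiers are spread across arms by chance and cause no systematic between-arm bias. The baseline AUDIT, DrInC and two-week timeline follow back, and the post-training question on motives, would allow a later look at implausible cases. This also stands, although the supplied text states no consistency rule that uses them. Nor does every over-reporter drink lightly: a worker who exaggerates symptoms may still drink heavily and be able to respond, in which case the attenuation is smaller.

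**Conclusion.** The point holds as a low-cost improvement to consider. The offer and pay come directly before 13 transparent, alcohol-only items, and the stated masking does not extend to those items. If some workers over-report symptoms to enter, the consequences are attenuation, misclassified strata and weaker generalisability, but not bias between arms. Under the assumptions shown, 5% to 20% false qualification takes 0.75 to 3 points off a 15-point difference. The documents give no rate from which to say where in that range, or outside it, the trial would fall.

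The conclusion rests on two inferences: that disorder status is an entry criterion, and that the Appendix A answers set the strata.

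A reader might also infer that false qualifiers would push up session completion and the share willing to take part again, both judged against 80% benchmarks. The documents do not support that. Genuine subjects receive the same pay, and a false qualifier could as easily drop out.

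**What to change.** In Appendix B, ask items 1 to 5 and item 7 first. Show item 6, with the study description and pay, only to workers whose answers already qualify. If interest in the study is itself a criterion, it can still be applied at that point. The cost is a reordering and one branch in an online form. The Phase 2 invitation repeats the pay and raffle terms, so nothing is withheld from those who enrol.

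Optionally, add short, separate, unscored tobacco and marijuana problem blocks beside item 7, shown to everyone, so that alcohol is not singled out. Keep them outside the disorder questionnaire: mixing them in would alter an instrument taken from a cited source and conflict with its alcohol-only introduction. The cost is a slightly longer screener.

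Reordering does not deal with repeat attempts, on which the supplied text is silent. It would also achieve less if the recruitment posting, which is not in the supplied text, already advertises the pay.

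### Feedback is described as a plain random half although AUD severity is known from the screener; stratifying that assignment on it and adding AUD stratum to the efficacy model would be a nearly free gain in balance and precision

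*Combined protocol and SAP*

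**What the plan says.** The screening paragraph of the Research Procedures places the AUD instrument before enrolment: "Subjects will also complete a questionnaire evaluating DSM-V criteria for alcohol use disorder". Appendix B lists it as item 7 of the screener, and Appendix A gives its 13 items.

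The baseline survey follows. Under Phase 1 the plan says "Approximately half of subjects will also be randomized to receive normative feedback on alcohol use as a part of the baseline survey", and the Normative Feedback paragraph says "Half of subjects will be randomly assigned to a normative feedback condition". Neither place names a stratum or a block. The other half receive feedback on an activity unrelated to alcohol, as an attention control.

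Training is assigned afterwards, under Phase 2: "Subjects will be randomly assigned to one of three training conditions using stratified sampling". The factor and the reason are given: "Sampling will be stratified based on alcohol use disorder status (e.g., moderate, severe) to ensure equal representation in each condition".

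The Data Analysis section plans mixed-effect models for intervention effects on alcohol use, with no heavy drinking days (yes or no) as the primary outcome. It gives no covariate list and no explicit feedback term. Baseline measures appear only in secondary prognostic analyses.

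**The concern.** AUD status is the one factor that the plan itself chooses to balance, and it does so for only one of its two randomised factors. Stratifying the training assignment cannot even out severity between feedback arms that already exist. Because feedback has its own attention control, a comparison of feedback with control is clearly intended.

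Severity is likely to predict heavy drinking. A chance gap in severity therefore shifts an unadjusted feedback contrast in that particular trial, and readers will question the result. Even with no visible gap, the unadjusted contrast carries between-stratum variation that could be removed. At stake are precision and credibility.

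**Working it through.** The plan states no sample size, severity mix, outcome rate or power, so there is no figure of its own to reproduce. What follows shows ranges under stated assumptions.

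**Inputs.** From the documents: 1:1 feedback allocation with no stratum named; AUD status known beforehand; two-sided alpha 0.05. Assumed: total N of 60, 120 or 240; severe share p = 0.5; no heavy drinking days in 40% of moderate and 15% of severe subjects.

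**Step 1: chance imbalance.** The SD of the difference in severe share between arms is sqrt(4p(1−p)/N). At p = 0.5 this is sqrt(1/N).

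| N | SD | 0.15/SD | P(gap ≥ 15 points), normal | P, simulation |
|---|---|---|---|---|
| 60 | 0.129 | 1.16 | 24.5% | 20–25% |
| 120 | 0.091 | 1.64 | 10.0% | 10–12% |
| 240 | 0.065 | 2.32 | 2.0% | 2–3% |

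The simulation range covers exact-half allocation and independent coin tosses.

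For a gap of 10 points or more, with a severe share of 30% to 50% and coin-toss allocation, simulation gives 42–52% at N=60, 29–37% at N=100, 13–18% at N=200 and 1.5–2.8% at N=500. The mean gap is zero throughout.

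**Step 2: effect of a gap.** With no true effect, a 15-point gap moves the contrast by 0.15 × (40 − 15) = 3.75 points.

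**Step 3: variance.**
- Overall rate: (0.40 + 0.15)/2 = 0.275, so the total variance is 0.275 × 0.725 = 0.1994.
- Within strata: (0.40 × 0.60 + 0.15 × 0.85)/2 = (0.24 + 0.1275)/2 = 0.1838.
- Ratio: 0.1994/0.1838 = 1.085, an excess of about 8%.

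**Step 4: what stratified assignment does to balance.** With blocks of 4 within each stratum, an unfinished block puts an arm at most one subject away from an even split. If the two strata err in opposite directions, the gap in severe share is 2/(N/2) = 4/N: 6.7 points at N=60, 3.3 at N=120 and 1.7 at N=240, as assigned.

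**Step 5: stratifying without adjusting.** An unadjusted two-proportion test still computes its standard error from the total variance. Simulated mean reported standard errors, simple against stratified allocation, are 0.115 and 0.114 (N=60), 0.0815 and 0.0811 (N=120), 0.0576 and 0.0575 (N=240). The true variance falls but the reported one does not, so the effective critical value rises to 1.96 × sqrt(1.085) = 2.04 and the type I error falls to about 0.041. Simulation gives 0.040–0.044.

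**Step 6: adjusting without stratifying.** With coin-toss allocation at N=60, simulation (200,000 runs) puts the variance of the stratum-adjusted contrast at 0.01267, against 0.01226 under stratified allocation: a ratio of 1.03, which moves closer to 1 at the larger sizes. The covariate alone therefore recovers nearly all of the gain.

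**Step 7: validity as written.** Over all allocations the unadjusted test has type I error of 0.050–0.052 (assumed rates 35% and 15%, N from 60 to 500).

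**The case against.** The strongest reply is that nothing here is an error. Simple 1:1 randomisation is valid, the efficacy aim is labelled initial, and choosing stratification instead is a design preference. That stands, and it sets the weight of the point.

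A reader might infer that the feedback comparison is biased, or that its false positive rate is inflated. The documents do not support that. Imbalance averages to zero and the overall type I error is about 0.05. Among only those allocations with a gap of 10 points or more, the unadjusted error is about 0.056–0.086 under the 35%/15% assumption, but that is a conditional figure.

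A reader might also infer that the plan rules out stratified feedback or an AUD covariate. It does neither; it is silent on both. The contrast with the training paragraph, and the word for an approximate half, make unstratified feedback the natural reading, not a certain one. The harm likewise depends on an unadjusted feedback contrast that the Data Analysis section does not spell out.

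Two practical objections also hold. Subjects can be lost between the baseline survey and the outcome, so balance at assignment may not persist in those analysed; a covariate acts on the analysed set. And the documents do not describe the baseline survey's randomiser, so the effort of feeding a score into it is not documented.

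**Conclusion.** The point holds as a small, nearly free improvement in balance and precision. Under the assumptions of half severe and 40%/15% outcome rates, the gain is removal of an excess variance of about 8%, and of a chance of a 15-point severity gap that runs from about 20–25% at N=60 to 2–3% at N=240. A smaller severe share, a weaker link between severity and outcome, or a larger N would shrink these figures; by N=500 even a 10-point gap is rare. Since the file gives none of these quantities, the size cannot be fixed more closely. Most of the precision gain comes from the analysis term; stratified assignment adds balance that can be seen in the baseline table.

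**What to change.** - **Allocation.** Assign feedback versus control feedback in permuted blocks within the screener AUD strata already used for training, and say so under Normative Feedback.
- **Analysis.** In the Data Analysis section, name AUD stratum as a fixed covariate in the efficacy model for both the feedback and the training effects. The calculations above are for a difference in proportions. If a logistic model is used, the adjusted odds ratio is conditional on stratum, so the effect measure should be stated.
- **If allocation is already complete.** Add the covariate alone.
- **If feedback was in fact stratified.** One clarifying sentence settles the allocation part; the covariate is still needed.

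The cost is scoring the screener to a severity category, passing it to the randomiser before feedback is assigned, and adding one model term. Subjects answer no extra questions.
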